10.3 Interim Analysis

There will be no interim analyses and, therefore, there are no criteria for early termination of the clinical investigation on statistical grounds.

11 GENERAL STUDY MANAGEMENT

11.1 Relevant Standards

This protocol has been developed in accordance with the following:

- ISO 14155:2011 Clinical Investigation of Medical Devices for Human Subjects
- ISO 11980:2012 Ophthalmic Optics - Contact lenses and contact lens care products
- ICH Harmonised Tripartite Guideline for Good Clinical Practice
- Declaration of Helsinki

The study will also be carried out in accordance with the Visioncare Research Quality Management System (ISO 9001:2008, ISO 13485:2012)

11.2 Ethical Review

The study protocol, patient instruction sheet, questionnaire and Informed Consent Form will be submitted to the REC/IRB (UK – NRES, US - STERLING). A favorable opinion will be received prior to undertaking the study. The approval letter should clearly mention the approval/favorable opinion of the protocol, the patient information sheet and informed consent form, including respective version dates.

If significant protocol changes which require the preparation of an amendment are necessary, written approval will be obtained prior to implementation.

11.3 Protocol Deviations

The investigators will not deviate from the protocol without written approval from Visioncare Research.

Any serious breaches of GCP that are likely to effect to a significant degree the safety, physical or mental integrity of the trial subjects or scientific value of the trial must be immediately notified to the Sponsor (and Visioncare, if reported by the investigator) to permit notification to the REC/IRB within 10 days after becoming aware of the breach.

In medical emergencies, the investigator will use their judgement and remove the subject from immediate hazard. Any significant changes or deviations in the protocol will be the subject of a protocol amendment and must be pre-approved by the REC/IRB.

If an unexpected deviation from the protocol occurs, the investigator must notify Visioncare Research immediately and the deviation from the protocol will be documented and resolved on a Protocol Deviation eCRF.

11.4 Premature Termination of the Study

The sponsor reserves the right to terminate the study at any time for any reason including adverse effects. The applicable authorities also have the right to terminate the study. If it is determined that an unanticipated adverse device effect presents an unreasonable risk, then the entire investigation or part of the investigation presenting the risk shall be terminated as soon as possible. A written statement fully documenting the reasons for such termination will be provided to the REC/IRB.

11.5 Source Documentation

The eCRFs will be considered the source document, unless otherwise documented. The sponsor's representatives (Visioncare Research) will be authorized to gain access to the source documentation for the purposes of monitoring and auditing the study (see sections 11.6 and 11.7).

The Source Document Record must be completed to comply with GCP guidelines. It is a permanent record within the patient's records/notes that documents the subject's involvement in a clinical research study.

Contents of the source document record:

- Study number
- Subject ID
- Confirmation that subject met eligibility criteria
- Confirmation that subject signed the informed consent
- Confirmation that subject received a signed and dated copy of informed consent
- Date enrolled
- Details of Solution (code) assigned
- Details of lenses worn on study
- General notes
- Adverse events
- Exit date
- Whether subject completed the study or discontinued
- Investigator's signature

The Source Document Record will be completed for each subject upon enrolment and then updated when required, e.g. when subject exits the study.

11.6 Monitoring

Investigational site monitoring will be performed by a qualified study monitor identified by the Sponsor or Visioncare Research. On-site visits will be completed at each site. The frequency and procedure of the monitoring visits will be documented in the monitoring plan which is in a separate document. The investigator will allow the study monitor and sponsor representatives or REC/IRB to observe procedures and inspect study records and subjects' medical records throughout the study to verify protocol compliance, case report completeness and investigational material accountability. Should the investigator be found to be non-compliant and unwilling or unable to convert non-compliant practices, Visioncare Research in consultation with the Sponsor will terminate the investigator's role in the investigation and the REC/IRB will be notified.

11.7 Audits

The Investigator shall permit Visioncare Research, the Sponsor, the REC/IRB and the appropriate regulatory authorities to inspect its facilities, equipment, and study-related records, data and other documents upon reasonable notice. In addition, the regulatory authorities or the REC/IRB may conduct such inspections as they deem necessary at any time whether or not advanced notice is given by them. The Investigator agrees to notify the Sponsor or Visioncare Research within 24 hours (or as soon as reasonably practicable) of the start of any unannounced inspection by the REC/IRB or the regulatory authorities or of the receipt from the REC/IRB or the regulatory authorities of a notice of inspection whether given in writing or orally. If such notice is in writing, a copy with any attachments thereto shall be provided to Visioncare Research or the Sponsor.

11.8 Records Retention

Investigators will be required to retain all records and the study file for a period of at least 10 years unless otherwise authorized by the Sponsor. As the clinical research organisation supervising the study, Visioncare Research will also retain the written records for the same period of time.

11.9 Confidentiality and Publication

By signing the Informed Consent form the subject authorizes the sponsor and the sponsor's representatives (Visioncare Research) to access their optometric clinical records. The authorization will be indefinite; however, subjects will have the right to reverse this authorization at any time.

All patient information will have the patient name (or any information that can identify the patient) removed before leaving the principal investigator's site.

In accordance with the VCR Confidentiality Policy, the data, information, and reports arising from this project are the property of the sponsor. VCR will not release to a third party any information arising from this study unless required to do so by a legal or regulatory body. The electronic records will also be handled in accordance with the UK Data Protection Act (1998).

The investigators will not be permitted to publish or present at scientific meetings results obtained from the clinical study without prior written consent from the sponsor.

13 ABBREVIATIONS

AE	Adverse event
CL	Contact lens
CRA	Clinical Research Associate
CRF	Case report form
CRO	Clinical Research Organisation
D	Diopter
eCRF	Electronic case report form
EDC	Electronic data collection
EDTA	ethylenediaminetetraacetic acid
GCP	Good Clinical Practice
HC	High Contrast
ICH	International Conference on Harmonization
IRB	Investigational Review Board
logMAR	Log of Minimum Angle of Resolution
MPS	Multipurpose solution
NRES	National Research Ethics Service
PHMB	polyheximethylene biguanide
REC	Research Ethics Committee
SH	Silicone hydrogel
SOP	Standard Operating Procedure
SOR	Spherical over-refraction
UK	United Kingdom
US	United States
VA	Visual acuity
VCR	Visioncare Research
WT	Wearing time

APPENDIX 1

Template Enrolment Log (Sample)

A maximum of 24 subjects may be enrolled. All subjects must be enrolled sequentially.
Subjects should only be entered onto the Enrolment Log once they have signed study Informed Consent Form.

Subject ID Site-Sub	Subject Name	Enrolment Date (Consent signed) (dd/mm/yy)	Subject Eligible	Reason if not eligible
01-01	John SMITH	10 / 06 / 17	Y/N	
01-01		/ /	Y/N	
01-02		/ /	Y/N	
01-03		/ /	Y/N	
01-04		/ /	Y/N	
01-05		/ /	Y/N	
01-06		/ /	Y/N	
01-07		/ /	Y/N	
01-08		/ /	Y/N	
01-09		/ /	Y/N	
01-10		/ /	Y/N	
01-11		/ /	Y/N	
01-12		/ /	Y/N	
01-13		/ /	Y/N	
01-14		/ /	Y/N	
01-15		/ /	Y/N	
01-16		/ /	Y/N	
01-17		/ /	Y/N	
01-18		/ /	Y/N	
01-19		/ /	Y/N	
01-20		/ /	Y/N	
01-21		/ /	Y/N	
01-22		/ /	Y/N	
01-23		/ /	Y/N	
01-24		/ /	Y/N	

ENROLMENT LOG OTES-3301 v1 dated 24 May 2017

APPENDIX 2

Template Kit-Box Accountability Form (Sample)

OTES-3301
Kit-box Accountability Log

Site #

Instructions:

1. When Kit-boxes are received at site, check the Kit-box number and record date of receipt.
2. When the Kit-box is dispensed record subject ID and date dispensed.
3. Record the date the Kit-box is returned by the subject to the site.
4. Record the date the Kit-box is returned to Visioncare Research.

Investigator's name: _____

Investigator's Signature _____ Date: _____

[Page 1 of 2]

APPENDIX 3

Template Source Document Record (Sample)

Source Document Record	
OTES-3301	
Sub ID: _____	Met Inclusion/Exclusion Criteria: YES / NO
Signed consent: YES / NO	Received sign/dated copy of consent: YES / NO
Enrolment Date: _____ / _____ / _____	
Multi-Purpose Solution Code: _____	
Lens Code: _____	
General Notes:	
Adverse Event Occurred? YES / NO (Record details of AE below)	
Adverse Event Resolved? YES / NO	
Exit Date: _____ / _____ / _____	Discontinued? YES / NO
Investigator signature: _____	

SAMPLE ONLY
DO NOT USE

APPENDIX 4

Grading Scales & Measurement Instructions

Variable	Assessment Method	Grading/Measurement System
Wearing Times		
Average Wearing Time	Typical time of day when lenses inserted and removed.	Time of day to nearest half hour
Comfortable Wearing Time	Typical time of day when subject first experiences lens awareness or irritation.	Time of day to nearest half hour when first aware of lenses OR 'Always comfortable' (tick-box)
Maximum Wearing Time	Maximum WT on a given day since last visit.	Hours to nearest half hour
Subjective Assessments		
Comfort	Assessed by subject.	0 to 10 scale 10 = cannot be felt
Vision		
Distance VA – High contrast	Measured using Snellen (or logMAR) chart.	Visual acuity (VA) to nearest letter
Vision Quality	Assessed by subject	0 to 10 scale 10 = perfect
Lens Fit - assessed using slit lamp		
Lens Centration	Lens centration will be recorded by degree and direction in the primary position.	0 Centered - optimal 1 Decentered slightly 2 Substantially decentered (≥ 0.5 mm) If decentered, direction(s) will be recorded as: Superior, Inferior, Nasal, Temporal
Corneal Coverage	Assessed in primary gaze.	Y Yes, full corneal coverage at all times N No, incomplete corneal coverage
Post-Blink Movement	Assessed immediately after the blink - lower lid to be depressed only if necessary for observation.	0 Insufficient, unacceptable movement 1 Minimal, but acceptable movement 2 Optimal movement 3 Moderate, but acceptable movement 4 Excessive, unacceptable movement
Lens Tightness – Push-up test	Assessed by digital push-up test (gentle push of the lens upward using the lower lid) with eye in primary gaze position and observing ease of push-up and speed of return to original position.	0 Insufficient, unacceptable movement 1 Minimal, but acceptable movement 2 Optimal movement 3 Moderate, but acceptable movement 4 Excessive, unacceptable movement

Variable	Assessment Method	Grading/Measurement System					
Overall Fit Acceptance	Assessed by the investigator based on lens fit alone (i.e. not comfort or vision).	0	Should not be worn	1	Borderline but unacceptable	2	Min. acceptable, early review
Biomicroscopy						3	Not perfect but OK to dispense
Stromal Edema	Assessed with indirect white light, medium-high magnification and observing any corneal haze against the pupil. More significant changes (e.g. striae, folds) can be observed with direct illumination.	4	Perfect	0	NONE: No corneal haze, normal transparency	1	TRACE: Just detectable haze
		2	MILD: Faint corneal striae (2 or fewer)	3	MODERATE: Pronounced corneal striae (3)	4	SEVERE: Folds in Descemet's membrane and ≥ 4 striae
		0	NONE: No injection present	1	TRACE: Slight limbal (mild segmented), bulbar (mild regional), and/or palpebral injection	2	MILD: Mild limbal (mild circumcorneal), bulbar (mild diffuse) injection
		3	MODERATE: Significant limbal (marked segmented), bulbar (marked regional or diffuse) injection	4	SEVERE: Severe limbal (marked circumcorneal), bulbar (diffuse episcleral or scleral) injection	0	NONE: No vascular changes
		1	TRACE: Vessel penetration <1.0 mm	2	MILD: Penetration of limbal vessels ≤ 1.5 mm	3	MODERATE: Penetration >1.5 mm to 2.0mm
Corneal Vascularization	Assessed using slit lamp with diffuse white light, low-medium magnification. The depth and location of any vascularization should also be recorded.	4	SEVERE: Penetration more than 2.0mm inside the limbus	0	NONE: Uniform satin appearance of conjunctiva	1	TRACE: Slight conjunctival injection without loss of texture
		2	MILD: Mild or scattered papillae/follicles less than 1mm in diameter	3	MODERATE: Significant papillae/follicles less than 1mm in diameter and/or marked conjunctival injection	4	SEVERE: Localized or generalized papillae/follicles 1mm or more in diameter
		0	NONE: Uniform satin appearance of conjunctiva	1	TRACE: Slight conjunctival injection without loss of texture	2	MILD: Mild or scattered papillae/follicles less than 1mm in diameter
		3	MODERATE: Significant papillae/follicles less than 1mm in diameter and/or marked conjunctival injection	4	SEVERE: Localized or generalized papillae/follicles 1mm or more in diameter	0	None
		1	Slight injection of conjunctival vessels	2	Mild injection	3	Moderate injection
Palpebral Conjunctival Hyperemia	Assessed with diffuse white light, low-medium magnification using CCLRU images for reference	4	Severe injection	0	None	1	Slight injection of conjunctival vessels
		1	Mild injection	2	Moderate injection	3	Severe injection
		2	Moderate injection	3	Severe injection	4	Severe injection
		3	Severe injection	4	Severe injection	0	None
		4	Severe injection	1	Slight injection of conjunctival vessels	2	Mild injection

Variable	Assessment Method	Grading/Measurement System
Corneal Staining Type	Assessed by sector with fluorescein, blue light, yellow filter and full beam using medium magnification. Cornea will be assessed by sector (C, N, T, I, S)	0 NONE: No staining 1 Micropunctate – Superficial, minute/fine/pinpoint punctate staining, includes superficial stippling 2 Macropunctate – Focal, ball-like punctate staining, includes moderate stipple staining 3 Coalesced macropunctate 4 Patch (> 1 mm)
Conjunctival Staining	Assessed by quadrant using fluorescein, blue light, yellow filter, low-medium magnification. Ignore conjunctival indentation with no staining.	0 None 1 Minimal diffuse punctate 2 Coalescent punctate 3 Confluent 4 Widespread confluent
Other Significant Findings	Describe finding and grade severity	0 NONE 1 TRACE 2 MILD 3 MODERATE 4 SEVERE
Lens Surface Characteristics		
Lens Surface Wetting	Lens surface wettability rated on the appearance of the lens surface and the drying time viewed with a slit lamp under low magnification.	0 VERY POOR: Immediately displaying non-wetting areas on lens surface. 1 POOR: Irregular surface appearance; drying time < interblink period. 2 ACCEPTABLE: Smooth surface appearance immediately after the blink becoming irregular with time; drying time \geq interblink period. 3 GOOD: Typical lens appearance with long drying time. 4 EXCELLENT: Appearance of a healthy cornea with very long drying time.
Film Deposits	Any film deposits (protein/lipid) attached to the front surface of the lens. Scan the entire lens surface (10- 20X) for the presence of deposits.	0 No film. 1 Slight film visible only under magnification. 2 Moderate film only under magnification. 3 Moderate film visible to the naked eye 4 Heavy film visible to the naked eye
White Spot Deposits	Assessed using slit lamp with white light, low-medium magnification	Number of white spot deposits

MEASUREMENT INSTRUCTIONS**DISTANCE VISUAL ACUITY**

Measure Visual Acuity (VA) to the nearest letter.

If the subject reads more than half of the letters on a given line, ask them to attempt the next line. Then if the subject is able to read letters on the next line assume that the previous line was correctly read for the purposes of recording VA.

EXAMPLE 1: If all six of the letters on the 6/9 line were correctly identified and the subject then correctly identified all but one of the six letters on the 6/7.5 line, record the acuity as:

6 / 7.5 - 1

EXAMPLE 2: If the subject correctly identified four of the six letters on the 6/6 line and two of the six letters on the 6/5 line were correctly identified, record the acuity as:

6 / 6 + 2

If necessary, VA can also be recorded on the eCRF in logMAR

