2.1 Primary Hypotheses

2.1.1 Efficacy Hypotheses

The Oté Sensation multi-purpose solution will be non-inferior to the Bausch & Lomb BioTrue solution in terms of:

Comfort (0-10), a non-inferior bound of 1.0 will be used.

Visual acuity (logMAR VA), a non-inferiority bound of 0.05 will be used

Wettability (0-4), a non-inferior bound of 0.5 will be used.

Deposits (*in situ* 0-4), a non-inferior bound of 0.5 will be used.

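### The visual acuity recording rule in Appendix 4 credits unread letters: a per-eye scoring error that would mask part of a solution difference only if scattered misses differ between arms

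*Combined protocol and SAP*

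**What the plan says.** Appendix 4, Measurement Instructions, Distance Visual Acuity, opens with "Measure Visual Acuity (VA) to the nearest letter". It then gives a progression rule, "If the subject reads more than half of the letters on a given line, ask them to attempt the next line", and a crediting rule: if letters on that next line are read, "assume that the previous line was correctly read for the purposes of recording VA".

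Two worked examples follow. In Example 1 the 6/9 line is read in full and "the subject then correctly identified all but one of the six letters on the 6/7.5 line"; the record is 6/7.5-1. In Example 2 the subject "correctly identified four of the six letters on the 6/6 line and two of the six letters on the 6/5 line"; the record is 6/6+2.

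The grading table in Appendix 4 allows either chart: "Measured using Snellen (or logMAR) chart". The closing line of the instructions also permits entry in logMAR. No conversion from Snellen notation to logMAR is given.

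Acuity is one of the primary efficacy hypotheses in section 2.1.1: "Visual acuity (logMAR VA), a non-inferiority bound of 0.05 will be used". Under section 10.2, non-inferiority is concluded if the upper one-sided confidence limit for the least-squares mean difference, Test minus Control, lies below +0.05 logMAR.

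**The concern.** The rule and the stated precision do not fit together. Example 1 deducts a letter missed on the last line read. Example 2 deducts nothing for two letters missed on the line before it. A subject who reads all of 6/6 and two letters of 6/5 gets the same record as one who misses two letters on 6/6, so the record cannot tell them apart.

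The rule also creates a jump. Four of six on 6/6 and none on 6/5 would be 6/6-2. Reading two letters on 6/5 makes it 6/6+2, so two letters read move the record by four. The text does not say how many letters on the next line trigger the credit.

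At stake is a primary endpoint with a narrow bound. Any difference between solutions that appeared as letters missed above the last line attempted would be partly erased before analysis, in the direction that favours non-inferiority. It could not be recovered later, because the missed letters are never recorded.

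**Working it through.** **Inputs from Appendix 4:** six letters per line; lines 6/9, 6/7.5, 6/6 and 6/5; progression when more than half of a line is read, so at least 4 of 6 with up to 2 missed. **From section 2.1.1:** bound 0.05 logMAR. **Assumed, because no conversion is given:** logMAR = log10(denominator/6), each letter being worth one sixth of the step to its line.

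**Reproducing the plan's record.** Four of six is more than half and letters were read on 6/5, so 6/6 is credited in full and two letters are added. The result is 6/6+2, as stated.

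**Letter values**
- 6/9 to 6/7.5: log10(9/7.5) = 0.0792; 0.0132 per letter
- 6/7.5 to 6/6: log10(7.5/6) = 0.0969; 0.01615 per letter
- 6/6 to 6/5: log10(6/5) = 0.0792; 0.0132 per letter

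**Example 2**
- As recorded: 0 - 2 × 0.0132 = -0.0264
- Letter by letter: 0.0969 - 4 × 0.01615 - 2 × 0.0132 = +0.0059
- Error: 0.0059 + 0.0264 = 0.0323 logMAR, which is the two missed letters, 2 × 0.01615

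**Two lines credited** (4 of 6 on 6/7.5, 4 of 6 on 6/6, 2 of 6 on 6/5): 2 × 0.0132 + 2 × 0.01615 = 0.0587 logMAR. The record is still 6/6+2.

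**Other charts.** With an assumed step of 0.1 logMAR, the largest credit on one line is:

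| Letters per line | Most that can be missed | Credit (logMAR) |
|---|---|---|
| 4 | 1 | 0.025 |
| 5 | 2 | 0.040 |
| 6 | 2 | 0.033 |
| 7 | 3 | 0.043 |
| 8 | 3 | 0.0375 |

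**From one eye to the mean difference.** Let c be the average credit per eye in an arm. The recorded mean is the letter-by-letter mean minus c, so the recorded difference is the letter-by-letter difference minus (c in Test - c in Control). If c is equal in the two arms, nothing is lost.

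Simulation shows when c differs. The main model has six-letter lines from 6/12 to 6/4, a logistic reading curve with slopes 0.02 to 0.04, and thresholds with mean -0.04 and SD 0.07. All these values are assumptions. Ranges cover the slopes and repeated runs.

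| Change in one arm only | Letter-by-letter shift | Shift as recorded | Hidden |
|---|---|---|---|
| Uniform threshold shift of 0.05 | 0.05 | 0.049-0.052 | none |
| Scattered misses 1% to 10%, start at 6/12 | 0.045-0.049 | 0.018-0.025 | 0.020 to 0.029 |
| Scattered misses 1% to 10%, start at 6/7.5 | 0.018-0.021 | 0.009-0.015 | 0.006 to 0.010 |

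For the 6/12 start the hidden part runs from 0.045 - 0.025 = 0.020 (44%) to 0.047 - 0.018 = 0.029 (62%). For the 6/7.5 start it runs from 0.021 - 0.015 = 0.006 (29%) to 0.019 - 0.009 = 0.010 (53%).

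A different assumed set-up shows how far the inputs matter. It used 0.1 steps from 0.5 logMAR, slopes 0.02 to 0.05, and no misses in the other arm:
- 5% misses: letter-by-letter 0.031-0.034, recorded 0.007-0.012
- 10% misses: letter-by-letter 0.077-0.081, recorded 0.032-0.043

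At 5% the share hidden is higher, 64-78% (0.0336 against 0.0120; 0.0314 against 0.0068), but the hidden amount is only 0.022-0.025 logMAR.

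**The case against.** A reader might set 0.032 against the 0.05 bound (0.0323/0.05 = 65%), or 0.0587 against it (117%), and infer that the rule can absorb most or all of the margin. The documents do not support that. The bound applies to a mean difference between arms. Both arms are scored by the same rule, are masked (section 3.1) and are randomized within site and lens type (section 3.2), so a common offset cancels. This objection stands, and the percentages should not be read as bias. Nor is two thirds a ceiling for one eye: the credit depends on letters per line and can accumulate over lines.

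Second, bias needs a solution effect that appears as scattered misses. The wetting scale in Appendix 4 describes non-wetting areas and surfaces that become irregular, which makes such misses plausible. Nothing in the documents says that they occur or that they differ by solution. This also stands.

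Third, the simulated sizes follow from chosen miss rates and a chosen starting line. The protocol states no starting line, and a start nearer threshold shrinks the effect. This stands too, and is why a range is given.

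Fourth, the nearest-letter instruction could refer only to the plus or minus letters on the final line. That softens the contradiction, but two different performances still share one record. Permission to enter logMAR changes the unit and does not switch off the crediting rule.

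A reader might also infer distortion of the count of lens acuity worse than 6/12 (section 10.2) or of the two-line comparison at exit (section 7.5.4). The same instruction feeds both, but no effect on either has been calculated, and the exit comparison uses the same rule at both visits.

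**Conclusion.** The point holds as a scoring defect with a conditional consequence. The certain part is that Example 2 credits two unread letters, and nothing else in the documents corrects for this. That misstates the eye by 0.032 logMAR, or 0.059 if two lines are credited, given six-letter lines and log10 steps.

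The conditional part is the effect on the non-inferiority test. There is none if misses above the last line attempted are equally common in both arms, or if the solutions differ by a uniform acuity loss. If one solution caused more scattered misses, the rule would pull the recorded difference toward zero. For misses rising from 1% to 10%, about 30-60% of the difference would be hidden, roughly 0.006-0.03 logMAR depending on the reading curve and starting line. Whether such a difference exists cannot be judged from the documents. The change is worth making because the error runs in the favourable direction and cannot be repaired after data collection.

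**What to change.** In Appendix 4, delete the sentence that treats the previous line as correctly read and credit only letters actually read. The existing rule for moving to the next line can stay. Rewrite Example 2 to show both the missed and the extra letters: 6/6 -2 +2. On the eCRF, record letters correct per line at each acuity measurement, and chart type and letters per line once per site. Compute logMAR centrally by one conversion stated in section 10.2.

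The cost is Appendix and eCRF wording and slightly more recording per acuity measurement. No new test is needed, since the letters are already being read.
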